#### **4.2 Primary Study Endpoints**

The primary study endpoints include tinnitus relief based upon questionnaires and tinnitus matching, tactile and auditory feedback, and the perception of discomfort during stimulation.

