#### **6.2.1 Transtympanic Cochlear Promontory Stimulation**

- a. At the first, second and third clinical appointment, the promontory stimulation equipment (Cochlear Corporation Nucleus Promontory Stimulator Z10012®; Cochlear Corporation, Melbourne, Australia) will be used. The initial session of promontory stimulation will define optimal stimulation parameters (i.e., current level, and frequency), where maximal tinnitus suppression occurs with minimal or no auditory percept. Stimulus amplitude will be increased slowly to establish threshold and maximum acceptable loudness. As an internal control function, testing will include a run of “on-off” simulations blinded to the subject, with patient blinded status to the “off” or “on” position of the stimulation machine. After these parameters are established, the patient will complete the THI, TFI, and VAS immediately prior to stimulation, during stimulation, and following completion of stimulation at 10-minutes, 1-hour, 24-hours, 48-hours, and 1-week following completion of stimulation (or prior to the next scheduled session of promontory stimulation, whichever occurs sooner), in addition to the recall survey, which is completed after a time period of one week (or prior to the next scheduled session of promontory stimulation, whichever occurs sooner). In addition, pitch and level matching of tinnitus will be completed immediately prior to the first promontory stimulation session and after the last session. Each patient will undergo three successive treatments separated by 7 days (+14/- 2 days). Prior to each treatment, the patient will receive an audiogram and DPOAE testing to document interval safety. At the conclusion of the study, subjects will be asked about their willingness to undergo surgical implantation of a device capable of long-term scheduled or on-demand electrical stimulation for tinnitus suppression.

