- b. The Cochlear Corporation Nucleus Promontory Stimulator Z10012 (Cochlear Corporation, Melbourne, Australia) will deliver stimulatory electric pulses. The stimulation will be delivered to the target sites using a transtympanic electrode kit, which contains a monopolar transtympanic needle electrode referenced to a surface electrode to be placed on the patient’s forehead. The tympanic membrane will be visualized with otomicroscopy with the patient in the supine position. Phenol will be applied to the tympanic membrane for local anesthesia. If residual irritation is perceived, EMLA cream will be used in the external auditory canal. The transtympanic electrode needle will be guided through the external canal aiming for the posteroinferior quadrant of the tympanic membrane. The needle will be stabilized in the ear canal using cotton packing or hearing aid mold putty and adhesive tape. Initially, an electrode impedance test will be performed

to validate proper placement and electrical contact of the electrodes. An indicator light will denote when impedances are not acceptable. If impedance values are not acceptable, a gentle repositioning of the proximal end of the needle electrode may be employed to ensure proper placement on the promontory. Otherwise, the needle electrode will be removed and reintroduced. Once proper electrical contact is validated, a calibration session to assess optimal stimulation parameters for the therapeutic session will be carried out using a range of 0 to 1 mA for pulse frequencies 100 Hz, 800 Hz and 1600 Hz. For each stimulus frequency, current level will be gradually increased to determine the following perceptual parameters: 1) Detection threshold or minimum threshold: first detection of the electrical stimulus (tactile or audible) as reported by the patient. 2. Maximum acceptable loudness level or discomfort level: when the applied current is perceived as loud but not uncomfortable. 3. The effective stimulation level will be determined to be 80% of the discomfort level or at minimum the minimum threshold level. The total duration of the electrical stimulation (at the optimal level) in each session will be ~30-60 minutes.

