#### b Data Analysis

THI, TFI and Tinnitus VAS scores will be analyzed based on numeric change over time after each promontory stimulation procedure. Data from the Audiograms / DPOAE will be assessed to ensure no baseline change in hearing has occurred as safety precautionary measures.

The NEO PI will be evaluated to determine correlation between tinnitus improvement scores and baseline personality assessment. Results of the NEO PI will not be used to screen for enrollment.

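### Scores taken during stimulation may reflect masking by an audible stimulus, and the plan neither ties percept to those ratings nor says how they will be used

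*Combined protocol and SAP*

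**What the plan says.** **Ratings.** Section 6.2.1(a) states that "the patient will complete the THI, TFI, and VAS immediately prior to stimulation, during stimulation, and following completion of stimulation", with the later ratings "following completion of stimulation at 10-minutes, 1-hour, 24-hours, 48-hours, and 1-week". Sections 4.1 and 7.1 give the same schedule.

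**Stimulation level.** Section 6.2.1(a) seeks parameters "where maximal tinnitus suppression occurs with minimal or no auditory percept". Section 6.2.1(b) sets the level from two calibration responses. The lower one is "first detection of the electrical stimulus (tactile or audible) as reported by the patient". The upper one, the discomfort level, is reached "when the applied current is perceived as loud but not uncomfortable". The rule is then: "The effective stimulation level will be determined to be 80% of the discomfort level or at minimum the minimum threshold level".

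**Endpoint.** Section 4.2 lists "tinnitus relief based upon questionnaires and tinnitus matching, tactile and auditory feedback, and the perception of discomfort during stimulation". It names no time point for relief.

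**Data and analysis.** Section 7.1 lists baseline characteristics and the scheduled questionnaires, with no item on what the subject perceives at a rating. Section 7.2 b says "THI, TFI and Tinnitus VAS scores will be analyzed based on numeric change over time", and the sentence goes on to refer that change to the time following each procedure. It does not mention during-stimulation scores or percept.

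**Related features.** Section 6.2.1(a) includes an on-off run to which the subject is blinded, as an internal control, with no outcome or analysis assigned. Section 4.1 names masking-level and residual-inhibition tests among the non-standard assessments, with no schedule or analysis.

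**The concern.** A sound in the ear can cover tinnitus while it lasts. The Background section counts masking among the existing strategies that make tinnitus easier to bear without removing it, and the case for an implant rests on electrical suppression being something more. If a subject hears the stimulus while answering a VAS, a lower score has two possible explanations, and the plan collects nothing with that rating to separate them.

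The during-stimulation rating is not a minor one. The Background reports that most patients have suppression only while current is applied and shortly afterwards. With no primary time point in Section 4.2, nothing keeps that rating from becoming main evidence of relief. Percept at the moment of rating also cannot be recovered afterwards if it was not recorded.

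**Working it through.** No stated figure of the plan is in dispute. The 24 subjects in Section 7.2 a come from THI change with no time point and do not enter here. The check compares the level rule with the stated aim, then asks which scores are exposed and which safeguards apply.

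**1. What the level rule implies.** Let T be the detection threshold, D the discomfort level and L the treatment level, all from Section 6.2.1(b). Reading the threshold as a floor:

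L = max(0.8 × D, T)

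Let r = D/T. The documents do not give r; a range of 1 to 3 is assumed. Then L/T = max(0.8 × r, 1):

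| r (assumed) | 0.8 × r | L/T |
|---|---|---|
| 1.0 | 0.80 | 1.0 |
| 1.25 | 1.00 | 1.0 |
| 1.5 | 1.20 | 1.2 |
| 2 | 1.60 | 1.6 |
| 3 | 2.40 | 2.4 |

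The set level is never below first detection, and it is above it whenever r exceeds 1.25.

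**2. Detection is not the same as hearing.** Let A be the lowest current heard as a sound. Because T may be felt or heard, A is at least T. Because D is defined by loudness, A is taken to be at most D. The stimulus is heard when A is at most L.
- If the first percept is a sound, A = T, so L is at or above A for every r.
- If the first percept is felt, L may lie on either side of A. The calibration as written does not ask for A separately.

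So the rule makes the stimulus perceptible at the time of setting. It makes it audible for those whose first percept is a sound, and leaves audibility unknown for the rest. The aim in 6.2.1(a), little or no sound heard, does not follow from the rule in 6.2.1(b).

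**3. Which scores are exposed.** Each session has one during-stimulation time and five later times, 1 + 5 = 6. Over three sessions that is 3 × 6 = 18 rating times, of which 3 are taken with current on. The other 15 are taken with the stimulator off.

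**4. Whether existing features separate masking from suppression at those 3 times.**
- *Auditory feedback (4.2):* named as an endpoint, but not scheduled with a rating. Perception can be transient, as the Background notes, so a calibration response does not show what was heard when the VAS was answered.
- *Blinded on-off run (6.2.1(a)):* a subject who hears the stimulus can tell on from off, so the blind fails in exactly the subjects of interest.
- *Masking-level and residual-inhibition tests (4.1):* no schedule or analysis links them to the ratings.
- *Analysis (7.2 b):* no rule for during-stimulation scores and no split by percept.

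**The case against.** The strongest reply is that the plan does not rely on the exposed scores. Section 7.2 b speaks of change following each procedure, five of the six times per session are free of concurrent masking, and the power calculation uses THI change rather than a during-stimulation VAS. The plan also intends to collect what subjects hear and feel, includes a blinded on-off run, and aims for little or no audible percept. The Background cites experience that stimulation is mostly unperceived or only briefly and slightly perceived.

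Much of this stands, and it rules out three stronger readings that a reader might infer:
- *That during-stimulation scores count as relief, or are pooled with later ones.* No section says so. The documents are silent, and the wording of 7.2 b leans towards the period afterwards.
- *That the study as a whole cannot tell masking from suppression.* The scores from 10 minutes onward are taken with the device off. Concurrent masking cannot explain them, although an after-effect of an audible stimulus is not excluded.
- *That percept is not collected at all.* Section 4.2 names it as an endpoint, and the calibration elicits it. What is missing is the link to each rating.

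What does not stand is the comfort drawn from past experience. Those reports describe other studies, while the rule here ties the level to a current reported as loud. Nor does silence in 7.2 b exclude the during-stimulation scores; it leaves their use open.

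**Conclusion.** The point holds for during-stimulation scores only. For those, masking by an audible stimulus is a plausible explanation that the plan does not address: the level is set at or above first detection, percept is not recorded with the rating, and no analysis rule covers these scores. Sections 6.2.1(a) and 6.2.1(b) also disagree on how audible the stimulus should be and must be reconciled by the sponsor; this review takes no position on which should give way.

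The reach is one of six on- or post-stimulation times per session, 3 of 18 over the study. No bias in scale points can be stated, since the documents give neither the share of ratings made while hearing the stimulus nor the effect of masking on a score. The conclusion assumes that some subjects hear the stimulus at the set level and that an audible signal can lower reported tinnitus. It does not depend on the assumed range of r, because the floor at detection applies for every r. This is a cheap improvement to the plan, not a defect that undermines the post-stimulation results.

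**What to change.** 1. With each during-stimulation rating, record the percept at that moment as heard, felt only or not perceived, and add the item to Section 7.1.
2. In Section 7.2 b, report during-stimulation change by percept and separately from post-stimulation change.
3. State that suppression will not be claimed from heard during-stimulation ratings alone. Use the 10-minute score, already collected, as supporting evidence free of concurrent masking.
4. Name the time point for relief in Section 4.2, and state the outcome and analysis of the on-off run.
5. Reconcile the aim in 6.2.1(a) with the level rule in 6.2.1(b).

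The cost is one extra item per during-stimulation rating, three per subject, one more table and a few sentences. The percept split has limits. Under the level rule the not-heard group may be small. Percept is also observed after treatment starts and is not randomised, so it may differ with current level and subject. The split should be labelled descriptive, and the claim should not rest on the not-heard group by itself. The 10-minute score has a limit too: an effect that ends soon after the current stops would be missed, so a null result there would not rule out suppression during stimulation.

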#### **6.2.2 ABR**

- a. A threshold ABR using a 37.7 rate click stimulus will be used for auditory brainstem response testing.

#### **6.2.3 DPOAEs**

- a. DPOAEs will be tested 1-10 kHz. Presence of DPOAEs will be determined using the following criteria: 6 dB SNR; absolute level of >=-10 dB.

### **6.3 Postprocedural appointment**

The primary investigator will visit with each patient one month after the three sequential electrical stimulation visits. The tympanic membrane will be evaluated for evidence of persistent perforation.

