## **STUDY SUMMARY**

Title: Cochlear Promontory Stimulation for Treatment of Tinnitus: Towards Developing an Implantable Device

IRB Protocol Number: 17-004832

Methodology: Prospective, investigational

Target subject accrual: 100

Expected duration of study: 10 years

Subject participation duration: 4 days [3 sequential clinic visits scheduled 7 days (+14/- 2 days) apart with a 3 month follow up visit]

Primary Objective: Use of a cochlear promontory stimulation electrode to provide safe, short term relief of tinnitus.

Secondary Objective: Map the optimum regions of the cochlear promontory in planning for an implantable electrical device for long term tinnitus suppression.

Principal Investigator: [name]

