will undergo three successive treatments separated by 7 days (+14/- 2 days). Prior to each treatment, the patient will receive an audiogram and DPOAE testing to document interval safety. At the conclusion of the study, subjects will be asked about their willingness to undergo surgical implantation of a device capable of long-term scheduled or on-demand electrical stimulation for tinnitus suppression.

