#### **5.4 Withdrawal of Subjects**

Patients who are not able to be evaluated on the date of appointment or those who should choose to withdraw for any reason will have the option to withdraw at any time.

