### 6.2 First Clinical Visit

1. Patients enrolled in the study will proceed to Mayo Clinic Otorhinolaryngology Department for additional evaluation. Candidate subjects will undergo a temporal bone CT, contrast enhanced head MRI, audiogram with immittance testing, pitch and level matching of tinnitus, and DPOAE and ABR testing prior to promontory stimulation. If during the course of the patient's visit, any of the exclusion criteria are met, the patient will be withdrawn from the study, and will be notified of this as soon as possible. If the patient has already had a temporal bone CT and/or a head MRI, they do not need to get another for this study.
  - a. The number and estimated length of each study visit

- i. 5 visits in total. The first visit would include a ~30 minute overview. The next visit would require ~2 min temporal bone CT, ~45 min MRI with contrast, ~45 min ABR, ~45 min audiogram and DPOAE, ~30-60 min of stimulation. The next 2 visits would require ~30-60 min stimulation. The last visit would require ~20 min for tympanic membrane evaluation for residual perforation and ~45 min for audiogram.

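### The only post-treatment visit is dated from completing three sessions, so a subject who stops after session 1 or 2 and does not return has no hearing or eardrum check scheduled after the last exposure

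*Combined protocol and SAP*

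**What the plan says.** **The visit after treatment.** Section 6.3 states: "The primary investigator will visit with each patient one month after the three sequential electrical stimulation visits". Its stated content is one item: "The tympanic membrane will be evaluated for evidence of persistent perforation". Section 6.2 adds a hearing test: "The last visit would require ~20 min for tympanic membrane evaluation for residual perforation and ~45 min for audiogram". The same section gives "5 visits in total" and places this visit last. The Study Summary describes "3 sequential clinic visits scheduled 7 days (+14/- 2 days) apart with a 3 month follow up visit", which is a different interval from section 6.3.

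**Hearing tests at other times.** Section 4.1 states: "Prior to each treatment, the patient will receive an audiogram and DPOAE testing to document interval safety". Section 6.2.1 repeats this. The screening battery in section 6.2 is also done before stimulation: "audiogram with immittance testing, pitch and level matching of tinnitus, and DPOAE and ABR testing prior to promontory stimulation".

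**Eardrum views at other times.** Section 6.2.1 has the eardrum inspected under the microscope as part of placing the needle at each session.

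**Leaving the study.** Section 5.4 says that "those who should choose to withdraw for any reason will have the option to withdraw at any time". It names no assessment on leaving and does not distinguish a subject who wants no more stimulation from one who wants no more contact. Section 6.2 says that a subject found to meet an exclusion criterion is withdrawn and told so; it names no assessment either.

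**The concern.** Safety is half of the primary objective in section 3, and section 7.2 b plans to use the audiogram and DPOAE data to show that hearing has not changed from baseline. That comparison needs a measurement after exposure. Because the routine tests come before each session, the effect of a session on hearing is measured only if the subject returns, either for the next session or for the last visit. Exposure starts with the first needle insertion, not with the third.

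A subject who has had enough after one or two sessions falls between these time points. Discomfort and a change in hearing are both plausible reasons for declining another session, and section 4.4 names the same two events as grounds for revising or ending the study. If such subjects are under-represented among those checked after their last exposure, the hearing and perforation results could look better than they are.

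**Working it through.** No figure in the plan depends on a formula here, so the check is a count of scheduled assessments.

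**Step 1: reproduce the visit count.** Section 6.2 itemises an overview (1), the first stimulation visit (1), further stimulation visits (2) and the last visit (1). 1 + 1 + 2 + 1 = 5, which agrees with the stated total. Exactly one visit follows the third session.

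**Step 2: count the checks by number of sessions received.** Inputs are sections 4.1 and 6.2.1 (tests before each session, microscopy at needle placement), and 6.2 and 6.3 (last visit). The time listing in 6.2 mentions only stimulation for the second and third stimulation visits; I have taken the explicit rule in 4.1 and 6.2.1 as governing.

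| Course | Checks between sessions | Hearing tests scheduled after last session | Eardrum checks scheduled after last session |
|---|---|---|---|
| Completes 3 sessions | Before sessions 2 and 3 | 1 | 1 |
| Stops after session 2, does not return | Before session 2 | 0 | 0 |
| Stops after session 1, does not return | None | 0 | 0 |
| Returns for pre-session tests, then declines stimulation | As above, by session | 1 | 0 |

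In the last row the eardrum count is zero because the microscopy belongs to needle placement, which does not take place.

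**Step 3: look for a provision that fills the zeros.** Sections 5.4 and 6.2 (withdrawal) trigger no assessment. Section 4.4 acts on the study as a whole and sets no subject-level check. Pitch and level matching after the last session measures tinnitus, not hearing safety. The post-session questionnaires measure tinnitus as well.

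**Step 4: what can be said about size.** The documents give no stopping rate, so the following assumes that 5% to 30% stop early and do not return, that all 100 subjects of the target accrual are stimulated, and that no event is seen in those checked.

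- Subjects without a scheduled check after the last session: 100 × 0.05 = 5 to 100 × 0.30 = 30.
- One-sided 95% upper bound for the event rate with zero events in n subjects: 1 − 0.05^(1/n). For n = 100 this is 3.0%; for n = 95, 3.1%; for n = 70, 4.2%.

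These bounds show only the loss of precision, which is modest. They hold if those who stop are like those who continue. They say nothing about bias, which depends on event rates in early stoppers, and the documents offer no basis for choosing those.

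**The case against.** The strongest reply is that section 6.3 promises the visit to each patient, and that the reference to three sessions merely dates it on the normal path. On that view early stoppers are included and only a detail is missing. This stands in part: the section does not exclude them, and a reader who infers that the plan restricts the visit to completers goes further than the text. But for a subject with one or two sessions the dating event never happens, so staff have no due date to work from.

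A second reply is that early stoppers are not unobserved. This also stands. In those who attend session 2, the pre-session audiogram and DPOAE test and the microscopy during needle placement show the state of the ear after session 1. A subject who comes back for testing and then declines has a hearing test after the last exposure. Discomfort during stimulation, an endpoint in section 4.2, is available for everyone stimulated. The statement that only completers are checked would therefore be wrong; what is missing is a check after the last session in those who do not return.

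A third reply is that section 4.4 responds to hearing loss that the surgeon documents or merely suspects, so it does not need a scheduled test. That is true of the trigger, but suspicion still depends on contact with the subject, and section 7.2 b needs measured data.

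Finally, the consent pages were not available for this review. Any statement there about follow-up after withdrawal could not be checked.

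**Conclusion.** The point holds as a gap in the schedule. For a subject who stops after session 1 or 2 and does not return, the number of hearing tests and of eardrum checks scheduled after the last exposure is zero, against one of each for a completer. That count rests on the documents alone.

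The effect on the safety result is a possible bias towards safe. It rests on the assumption that stopping is related to discomfort or hearing change, which is plausible but not stated in the documents. A reader might go on to infer that the reported hearing-loss or perforation rate will be understated by some particular amount. The documents do not support that: they give no stopping rate and no event rates by number of sessions, so the size is unknown. The 1.6% risk of persistent perforation in section 4.5 cannot be split between completers and early stoppers.

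The change is worth making because it protects half of the primary objective and uses a visit that is already planned. It concerns whose outcomes are collected and when, not treatment.

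**What to change.** - **Sections 6.2 and 6.3:** date the existing last visit, with its eardrum evaluation and audiogram, from the last stimulation session or needle insertion that the subject received. State that it applies to every exposed subject, however many sessions were completed.
- **Section 5.4:** separate stopping stimulation from withdrawing consent for follow-up. Keep subjects in the first group in the planned last visit and in the questionnaires already scheduled after their last session.
- **Interval:** section 6.3 gives one month and the Study Summary gives 3 months. The sponsor must reconcile these, and the visit list in section 6.2 with them. This review takes no position on which is right.

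The cost is protocol wording plus some effort to bring back subjects who stopped. Those who withdraw consent for follow-up will still be missing.
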